## 8.2. Statistical analysis

Statistical assessments of dosage normalized levodopa AUC0-inf, AUC0-last, AUC0-16, AUC0-2, AUC2-16, and AUC8-16 by analysis of variance (ANOVA) will be made on the logarithmic values, with back-transformation to nominal values of point estimates and confidence interval (CI). These variables will also be tested with dosage un-normalized values. The terms to be used in the ANOVA model will be sequence, patient within sequence, period, and formulation (i.v. or s.c. Infudopa and Duodopa; test and reference, respectively).

The statistical method for testing relative dosage normalized levodopa bioavailability will be based on the 90% CI for the ratio of the population means (test/reference). These statistical tests will also be done with dosage un-normalized values. The acceptance range for AUC ratio of the 90% CI for levodopa will be 0.80 to 1.25. These tests will be performed for Treatment 1 (i.v.) and Treatment 2 (s.c.) vs. Treatment 3 (Duodopa; reference) comparison, and for Treatment 1 (i.v. reference) vs. Treatment 2 (s.c.).

For each individual will be calculated the COV (coefficient of variation or % standard deviation; SD) for plasma concentration between 2 and 16 h by dividing the SD for each individual curve with the mean value of plasma concentration between 2 and 16 h. The mean value of plasma concentration will be calculated for each curve as AUC2-16/14. Basic statistics for the COV will then be calculated per treatment group. The one-sided 90% CI of the intersubject COV will be calculated for Treatment 1 (i.v.) and Treatment 2 (s.c.) vs. Treatment 3 (Duodopa; reference) comparison, and for Treatment 1 (i.v. reference) vs. Treatment 2 (s.c.). It will also be tested with paired t-tests if there are significant differences in intersubject COV between treatments (i.v. vs. Duodopa, s.c. vs. i.v., and s.c. vs. Duodopa).

The level of significance will be p=0.05.

Safety will be summarized with the standard set of AE summary tables, and descriptive summary statistics of vital signs by visit and change from baseline.

The local tolerability will be documented with photographs, which will be evaluated by a dermatologist. Pre-defined local tolerability AEs will be documented by the investigator, and tenderness and pruritus with VAS by the subjects. Local tolerability will be presented with descriptive summary statistics of these variables by visit and change from baseline.

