There is no documentation available showing the levodopa bioavailability for Duodopa vs. the i.v route. Based on the needed dosages of a levodopa solution administered i.v. to patients previously treated with Duodopa at the Linköping University Hospital, it may be estimated that Duodopa administered enterally is about 75% bioavailable as compared to i.v. administration. Experience from patients following s.c. administration at the same center suggests that equal doses of s.c. and Duodopa administrations can be used (Dizlin, data onfile). This suggested that the bioavailability of s.c. formulation may be in the range 75-100% when considering a complete dosage interval of a day. The dosage calculations for s.c. administration when starting the trial was hence based on the assumption of a 75% bioavailability. Analysis of data from the first 5 interim analysis patients, however, revealed that the absolute bioavailability of Infudopa s.c. is 100% vs. the i.v. standard, i.e. higher than expected (Clinical Study Interim Report 2019-01-15). Also Duodopa had a slightly higher absolute bioavailablity than the previous estimation (82% vs. i.v.). The ratio between LCIG and s.c. Infudopa levodopa bioavailability based on AUC 0-infinity was 0.78 and based on AUC 0-16 h 0.86. The AUC 0-16h was regarded as the most relevant variable for dose adjustment, because this is the time interval when the patient needs the optimal effect. Hence it was decided, that for the second part of the trial the dosage of Infudopa s.c. will be based on the assumption of an 86% bioavailability of Duodopa as compared to Infudopa s.c..

The aim of the present study will be to compare the pharmacokinetic and safety profile of Infudopa administered i.v. and s.c. with Duodopa administered enterally in patients with late stage Parkinson's disease.

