## 2. STUDY OBJECTIVES AND ENDPOINTS

### 2.1. Primary objective

• To demonstrate that doseadjusted Infudopa s.c. yield steady state plasma concentrations of levodopa that are equivalent with those of Duodopa, that the variability in plasma concentrations during the dosage interval is non-inferior to that obtained with Duodopa., and to establish the absolute bioavailability of levodopa when given as Infudopa s.c. or Duodopa as compared to Infudopa i.v.

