# 8. STATISTICS

## 8.1. Sample size calculation

Sample size determinations are based on the primary pharmacokinetic variable from a similar study (Nyholm et al, 2013) regarding 16-hour intestinal infusion of Dudopa in advanced Parkinson's disease patients. Data from the 5 interim analysis patients are also used. A standard t-test model with continuity correction has been used (Microsoft Excel program, Pharm Assist Sweden AB). Z-alpha level was 1.96 and Z-beta level was 0.84 for equivalence testing of 90% CI of 0.80 to 1.25, and Z-alpha level was 1.65 and Z-beta level was 0.84 for non-inferiority testing of 90% CI of 0.80 to 1.25.

The test suggests that 14 subjects are appropriate for the test of dose-normalized AUC 0 to infinity of levodopa. This number of subjects is valid both based on the Nyholm et al. 2013 data for LCIG (COV 24.5%), and the data in the interim study (COV 17.0% allowing as a safety margin for a 40% higher COV, 23.8%, giving n=14).

For the non-inferiority test of intersubject coefficient of variation (COV) the sample size estimation suggests 18 subjects to be included.

Based both on the levodopa dose-adjusted AUC 0 to infinity and the intersubject COV it is planned that 22 subjects will be recruited to the study, also allowing for 4 drop-outs.

Clinical Study Protocol	Study code:	IPO-001
	Version No:	5.1
	Date:	26 MARCH 2019

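### The equivalence test is sized on dose-normalised AUC0-inf as if the ratio were 1, but the protocol's interim figures imply 1.28 (s.c.) and 1.22 (i.v.), and no deciding AUC is named

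*Protocol*

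**What the plan says.** Section 2.1 opens the primary objective with: "To demonstrate that doseadjusted Infudopa s.c. yield steady state plasma concentrations of levodopa that are equivalent with those of Duodopa". The same sentence goes on to non-inferior variability and to the absolute bioavailability of s.c. Infudopa and Duodopa against i.v. The synopsis instead makes equivalence of both i.v. and s.c. to Duodopa primary.

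Section 8.1: "The test suggests that 14 subjects are appropriate for the test of dose-normalized AUC 0 to infinity of levodopa". It uses Z-alpha 1.96 and Z-beta 0.84, with a COV of 24.5% from an earlier Duodopa study, or the interim 17.0% raised to 23.8%. It states no true ratio. The recruitment figure of 22 is the 18 from the COV non-inferiority test plus 4 drop-outs.

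Section 8.2 lists six AUC intervals and describes the test: "The statistical method for testing relative dosage normalized levodopa bioavailability will be based on the 90% CI", taken for the test/reference ratio. It then adds: "These statistical tests will also be done with dosage un-normalized values". One rule covers all of them: "The acceptance range for AUC ratio of the 90% CI for levodopa will be 0.80 to 1.25". Section 6.1 names AUC as primary without giving an interval or saying whether it is normalised.

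Section 1.3 reports the five interim patients: "The ratio between LCIG and s.c. Infudopa levodopa bioavailability based on AUC 0-infinity was 0.78 and based on AUC 0-16 h 0.86". It also puts Duodopa at 82% of i.v. Section 5.1.1 gives the AUC0-16 ratio of Duodopa to i.v. as 0.81, and sets the s.c. and i.v. totals at 86% and 81% of the Duodopa dose to offset these differences.

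**The concern.** The Infudopa doses are scaled down because Duodopa is less bioavailable. Dividing AUC by dose undoes that scaling, so the dose-normalised ratio returns the bioavailability difference that the sponsor has already measured and dosed around. For s.c. AUC0-inf, that known difference lies beyond the upper limit. Section 8.1 took the COV from the interim data but not the ratio.

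Two things are at stake. The power calculation for equivalence describes a test expected to fail even when dosing works as intended. And if the normalised and as-dosed versions disagree, as the interim figures predict, the protocol does not say which one answers the primary objective. The choice would then be made after seeing the data.

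**Working it through.** **Step 1. Reproduce n=14.** A paired t-test size, n = (t(0.975) + t(0.80))² × COV² / 0.20², is iterated on n-1 degrees of freedom. At n=14 the t values are 2.160 and 0.870.
- COV 24.5%: (3.031)² × 0.0600 / 0.04 = 13.8, so 14.
- COV 23.8%: (3.031)² × 0.0566 / 0.04 = 13.0, so 14 after rounding up.

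The 0.20 is the distance from 1 to 0.80 on the raw scale (1.05 is equally far from 1.25). A ratio of 1.22 would leave 0.03 to the upper limit, and 1.28 leaves nothing, so no sample size gives 80% power there.

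**Step 2. Ratios implied by sections 1.3 and 5.1.1 (test/Duodopa).**
- Dose-normalised s.c.: AUC0-inf 1/0.78 = 1.282; AUC0-16 1/0.86 = 1.163.
- Dose-normalised i.v.: AUC0-inf 1/0.82 = 1.220 (basis assumed); AUC0-16 1/0.81 = 1.235.
- As-dosed s.c.: AUC0-16 0.86/0.86 = 1.00; AUC0-inf 0.86/0.78 = 1.103.
- As-dosed s.c. AUC8-16: the protocol gives no interim ratio. Suppose s.c. is at steady state by 8 h. For a Duodopa rate of 100 mg/h, the Duodopa total is 100 × (16 - 0.1375) + 110 = 1696 mg. The s.c. total is 0.86 × 1696 = 1459 mg, and its hourly rate is 1459 / (16 - 0.163 + 1.55) = 83.9 mg/h. The bolus times follow from the stated pump speeds (800 mg/h for both). The level ratio is then 0.839/0.78 = 1.076, about 1.08.

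**Step 3. Chance that the 90% CI lies inside 0.80-1.25, n=18.** Simulated on the log scale, 400,000 trials per cell. The protocol does not say what its COV measures, so three readings are used: SD of the log ratio 0.169 (17% as SD of the paired difference, 17 df), 0.241 (24.5% read the same way, 17 df) and 0.341 (24.5% as within-subject COV, √2 × 0.241, 32 df).

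| Variable (test/Duodopa) | Ratio | SD 0.169 | SD 0.241 | SD 0.341 |
|---|---|---|---|---|
| s.c. AUC0-inf, dose-normalised | 1.282 | 1% | 2% | 3% |
| i.v. AUC0-inf, dose-normalised | 1.220 | 15% | 11% | 9% |
| s.c. AUC0-16, dose-normalised | 1.163 | 54% | 34% | 22% |
| i.v. AUC0-16, dose-normalised | 1.235 | 9% | 7-8% | 7% |
| s.c. AUC0-16, as dosed | 1.00 | >99% | 97% | 71% |
| s.c. AUC0-inf, as dosed | 1.103 | 92% | 68% | 44% |
| s.c. AUC8-16, as dosed | 1.08 | 97% | 79% | 53% |

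With 22 completers the s.c. dose-normalised AUC0-inf figure is still 1-2%.

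**Step 4. Allow for five interim patients.** The true log ratio is spread around the interim value with standard error SD/√5 (flat prior), COV 17% to 24.5% under both readings, n=18. The chance of passing dose-normalised AUC0-inf becomes about 14-16% for s.c. and 21-31% for i.v. This covers sampling error only. Section 1.4 says that the restart uses a new s.c. buffer with 20% of the earlier citrate, and any effect of that cannot be quantified from the protocol.

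**The case against.** A reader might infer that the trial is bound to miss its primary objective even when plasma levels match. The protocol does not support that. Section 8.2 runs the same model and limits on un-normalised AUC, including AUC0-16 and AUC8-16, and nothing there calls the dose-normalised version decisive. An analysis plan that is not shown may rank the tests.

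Other points also stand:
- The second half of the objective in section 2.1 needs dose-normalised AUC, so that analysis belongs in the plan.
- The binding 18 comes from the COV test, not from AUC0-inf.
- The true ratio of 1 is inferred by reproducing n; it is not written.
- The i.v. ratio lies inside 1.25, so failure is very likely but not near certain. Equivalence for i.v. is primary only in the synopsis.
- The ratios rest on five patients and an earlier s.c. buffer.
- Section 5.1.2 allows infusion rates to be changed during treatment, so as-dosed AUC partly reflects those changes and an expected ratio of 1.00 assumes none.

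These limit the claim but do not remove it. The only equivalence variable that was sized is one that the protocol's own figures expect to fail. The sponsor relied on the same five patients to reset the doses. A later ranking of tests would not correct the calculation in section 8.1.

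**Conclusion.** The concern holds in this form: section 8.1 claims 80% power for a variable on which, at the interim ratios and n=18, the test would pass about 1-3% of the time for s.c. and 9-15% for i.v. With allowance for five interim patients, this is about 14-16% and 21-31%. The figures assume log-normal AUC, the COV readings shown, and AUC0-inf as the basis of the 82%; the AUC0-16 figure for i.v. (1.235) gives no better result. The sized variable also cancels the dose adjustment that the objective in section 2.1 relies on, and the protocol leaves open which of six intervals in two versions decides. The defect lies in the choice and sizing of the deciding variable. It does not show that the trial as a whole must fail, because the matching as-dosed test is already planned.

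**What to change.** - In sections 6.1 and 8.2 and the synopsis, name un-normalised (as-dosed) s.c. versus Duodopa exposure as the deciding equivalence variable, with limits 0.80 to 1.25. AUC0-16 is preferable because the dose factor was set on it: expected ratio about 1.00 if infusion rates are not changed, power about 71% to over 99% at n=18.
- If AUC8-16/8 is preferred as the steady-state measure, state its own expected s.c. ratio. On the assumption in the working it is about 1.08, with power about 53-97%.
- Keep dose-normalised AUC ratios as bioavailability estimates with 90% CI and no acceptance range.
- Restate section 8.1 for the chosen variable and its expected ratio, and say whether the COV is within-subject or that of the paired difference, since the power range turns on this.
- Say how the first five patients, dosed s.c. on a 75% assumption (section 1.3), enter the as-dosed analysis, and how changes of infusion rate are handled.
- Align the synopsis and section 2.1 on whether i.v. equivalence is primary.

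The cost is wording only: no new data or assessments. The planned 18 need not change on this account, because it comes from the COV test. The restated section 8.1 should give the power that 18 provides, which falls below 80% for AUC0-16 only if the 24.5% is a within-subject COV.

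### The COV comparison is specified with a one-sided 90% interval, literally 10% error, but was sized at one-sided 5%; it also lacks a stated upper limit and is labelled intersubject although defined within each patient's curve

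*Protocol*

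**What the plan says.** The primary objective (synopsis and section 2.1) includes showing that the variability of plasma levodopa over the dosage interval is non-inferior to Duodopa. Section 6.1 lists the COV as a primary variable.

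- **Definition.** Section 8.2 computes a COV for each individual by "dividing the SD for each individual curve with the mean value of plasma concentration between 2 and 16 h". That mean is AUC2-16/14 of the same curve.
- **Interval.** Section 8.2, repeated in the synopsis: "The one-sided 90% CI of the intersubject COV will be calculated for Treatment 1 (i.v.) and Treatment 2 (s.c".), each versus Duodopa, and also i.v. versus s.c.
- **Additional test.** "It will also be tested with paired t-tests if there are significant differences in intersubject COV between treatments".
- **Level.** "The level of significance will be p=0.05". Sidedness is not stated.
- **Sizing.** Section 8.1: "Z-alpha level was 1.65 and Z-beta level was 0.84 for non-inferiority testing of 90% CI of 0.80 to 1.25", and "For the non-inferiority test of intersubject coefficient of variation (COV) the sample size estimation suggests 18 subjects to be included". With 4 drop-outs allowed for, this gives 22.
- **Limit.** Section 8.2 ties its acceptance range to exposure only: "The acceptance range for AUC ratio of the 90% CI for levodopa will be 0.80 to 1.25". It gives no limit for the COV.

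**The concern.** Three things about one primary comparison do not fit together.

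1. **Error rate.** The sizing uses one-sided 5%. The analysis text names an interval that, taken at its word, has one-sided 10% error.
2. **Criterion.** The only limits attached to non-inferiority are 0.80 to 1.25, in section 8.1. Lower variability is better, so only an upper limit has meaning. Section 8.2 names none and does not say whether the interval is for a ratio or a difference.
3. **Label.** An intersubject COV is one number per treatment group. The quantity defined in section 8.2, and the one the objective needs, is variability over time within a patient.

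At stake is the claim that Infudopa is at least as stable as Duodopa. The COV comparison also sets the sample size: it asks for 18 subjects, the AUC comparison for 14. The trial is open-label, so a level or limit settled after data are seen would look data-driven.

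**Working it through.** **Inputs.** From section 8.1: Z-alpha 1.65 and Z-beta 0.84 (non-inferiority); Z-alpha 1.96 and Z-beta 0.84 (equivalence); AUC COV 24.5% and 23.8%; n = 14 (AUC) and n = 18 (COV). The SD behind the 18 is not given. Assumption: delta = 0.20, the distance from 1 to 0.80.

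**Step 1: reproduce the plan's own figure.** Section 8.1 mentions a t-test model with a correction. The formula n = (SD × (Zα + Zβ)/delta)² + Zα²/2 gives, for AUC:

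- SD 0.245: (0.245 × 2.80/0.20)² + 1.96²/2 = 11.76 + 1.92 = 13.69, rounded up to 14.
- SD 0.238: (0.238 × 2.80/0.20)² + 1.92 = 11.10 + 1.92 = 13.02, rounded up to 14.

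Both match the stated 14, so this formula is a reasonable stand-in for the sponsor's program.

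**Step 2: the 18.** Without an SD it cannot be reproduced. Solving backwards for 17 < n ≤ 18 at Zα + Zβ = 2.49:

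- With the correction (1.65²/2 = 1.36): SD from 0.20 × √(17 − 1.36)/2.49 = 0.318 to 0.20 × √(18 − 1.36)/2.49 = 0.328.
- Without it: SD from 0.331 to 0.341.

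A different delta changes the implied SD but not the sample sizes or powers below.

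**Step 3: the two error rates.**

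- Z = 1.65: one-sided error 1 − Φ(1.65) = 0.0495.
- One-sided 90% interval: z = 1.2816, one-sided error 0.10.
- Simulated at the margin with a t-based bound and n = 18: 0.0995 for the one-sided 90% bound, 0.0498 for the one-sided 95% bound.

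**Step 4: what the literal interval would mean for size and power.**

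- Simple scaling: 18 × [(1.2816 + 0.84)/(1.65 + 0.84)]² = 18 × (2.1216/2.49)² = 13.1.
- With the implied SDs: 12.17 to 12.90 with the correction, 12.34 to 13.07 without. That is 13 to 14 subjects.
- Power by shifting z: Φ(1.65 + 0.84 − 1.2816) = Φ(1.208) = 0.887.

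| Power at n = 18 over the implied SDs | Normal | t, 17 df |
|---|---|---|
| One-sided 5% | 0.80 to 0.85 | 0.77 to 0.82 |
| One-sided 10% | 0.89 to 0.92 | 0.87 to 0.91 |

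The sizing in section 8.1 therefore belongs to a one-sided 95% bound, not a one-sided 90% bound.

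**Step 5: which COV.** Section 8.2 divides each curve's SD by that curve's mean, giving one value per patient and treatment. A paired t-test needs exactly that. A true intersubject COV leaves nothing to pair. The definition and the test therefore point to the within-curve quantity, while the label in the synopsis, 8.1 and 8.2 names another. Section 8.1 also uses COV for AUC, so the text does not show which variability produced the 18.

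**The case against.** The strongest reply is that nothing is wrong but wording. Section 8.1 itself couples a 90% interval with Z-alpha 1.65, so in this protocol a 90% interval for non-inferiority may mean one limit of a two-sided 90% interval. That is 5%, and it agrees with the sizing and is compatible with the 0.05 level if that is one-sided. Section 8.2 also says only that the interval will be calculated, not that it decides non-inferiority. This reading is plausible and probably shows the intent. It does not remove the conflict: one-sided 90% has a fixed meaning, and it is the only interval planned for the COV.

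On the limit, one can argue that a one-sided interval and a 0.80 to 1.25 range leave only 1.25. That is a fair inference, but a primary criterion should be stated.

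On the label, the definition and the pairing largely settle what will be analysed. A reader might infer that the wrong variability will be computed; the documents do not support that. What stays open is the input to the sample size.

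A reader might also fault the paired t-test for ignoring period, or for testing raw values against a ratio margin. The protocol introduces it as an additional test of difference and states no scale. Model and scale can be left to the analysis plan.

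**Conclusion.** The provision is wrong as written and needs correcting. Taken literally, the interval in section 8.2 and the synopsis has 10% one-sided error where section 8.1 planned 5%. It corresponds to 13 to 14 subjects rather than 18, or to about 87 to 92% power at 18. These figures hold only on the literal reading and rest on a formula inferred from the AUC calculation and an SD solved backwards from 18.

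Two stronger conclusions are tempting. One is that the trial will in fact run at a doubled error rate; the documents do not establish this, because the looser reading gives 5%. The other is that 18 is the wrong number; it cannot be reproduced because its SD is not stated, but that does not show an error. What is established is that the level is contradictory, the upper limit is not stated where the analysis is defined, and the label contradicts the definition.

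**What to change.** - In section 8.2 and the synopsis, state that non-inferiority is shown if the upper limit of the two-sided 90% confidence interval (the one-sided 95% bound) for the test/Duodopa ratio of within-curve COV over 2 to 16 h is below 1.25.
- In section 8.1, replace the two-sided range for non-inferiority with that single upper limit.
- In the synopsis, 8.1 and 8.2, replace intersubject with intra-individual (within-curve).
- In section 8.1, confirm that 18 was derived from the within-curve COV and give the SD used.

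Analysing ln(COV) in the ANOVA already planned for AUC is one acceptable way to obtain the ratio and its interval, but it is not required.

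**Cost.** This is an amendment of wording. Compared with the literal one-sided 90% bound, the distance from estimate to limit grows by a factor of 1.645/1.2816 = 1.28 on the normal scale. N stays at 18 if it came from the within-curve COV, with power of about 77 to 85% over the implied SDs. If it came from another quantity, the sample size has to be recalculated.

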# 6. STUDY MEASUREMENTS AND VARIABLES

## 6.1. **Primary variable(s)**

The steady-state plasma concentration of levodopa, the area under plasma concentration versus time curve (AUC), and the coefficient of variation (COV) for plasma concentrations during the dosage interval in the subjects are the primary efficacy variables of the study. Also refer to Table 8.

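### The variability test and its n=18 are tied to an 'intersubject' COV, contradicting the within-patient COV that the objective and Section 8.2 define; alpha conflicts and the input behind 18 is not given

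*Protocol*

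**What the plan says.** Three places describe variability within a patient's treatment day.

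- Section 2.1 sets out to show "that the variability in plasma concentrations during the dosage interval is non-inferior to that obtained with Duodopa".
- Section 6.1 lists, with steady-state concentration and AUC, "the coefficient of variation (COV) for plasma concentrations during the dosage interval in the subjects are the primary efficacy variables".
- Section 8.2 begins: "For each individual will be calculated the COV (coefficient of variation or % standard deviation; SD) for plasma concentration between 2 and 16 h". It divides the SD of each curve by that curve's mean (AUC2-16/14) and summarises the result per treatment.

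The inferential text then changes the quantity.

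- Section 8.2: "The one-sided 90% CI of the intersubject COV will be calculated", for i.v. and s.c. against Duodopa and for s.c. against i.v.
- Section 8.2, next sentence: "It will also be tested with paired t-tests if there are significant differences in intersubject COV between treatments".
- Section 8.1: "For the non-inferiority test of intersubject coefficient of variation (COV) the sample size estimation suggests 18 subjects to be included".

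The Statistical methods part of the Synopsis repeats the wording of 8.2. The label occurs six times, twice in each of the three places, and is never defined or linked to the individual COV.

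On error rate, 8.1 gives Z-alpha 1.65 and Z-beta 0.84 for non-inferiority, with limits 0.80 to 1.25. Section 8.2 gives a one-sided 90% CI and a significance level of 0.05, and ties the 0.80 to 1.25 range to the AUC ratio only.

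**The concern.** The hypothesis is that one patient's level stays as steady on Infudopa as on Duodopa. Spread between patients is a different property: a treatment could give every patient a flat curve and still show a wide spread of levels across patients, or the reverse. The sentences stating the decision rule for a primary variable, and the sample size that sets recruitment (18 + 4 drop-outs = 22), carry the name of the wrong quantity.

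The trial is open-label and Section 8.4 plans another interim look at PK data. A primary variable with two possible meanings, two possible alphas and a sample size of unknown origin leaves a choice to be made after data have been seen.

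**Working it through.** **1. Which quantity can the stated methods use?** A paired t-test needs one value per patient per treatment. The individual 2-16 h COV supplies that; an intersubject COV supplies one value per treatment and no pairs. Section 8.1 says a t-test model was used for sample size, which also concerns means of patient-level values. So the methods fit the individual COV and the label does not.

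**2. Alpha.** A one-sided 90% CI has 10% error. Z-alpha 1.65 is one-sided 5%, which corresponds to the upper limit of a two-sided 90% CI. The stated significance level is also 5%.

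**3. Reproducing n=14 (AUC0-inf).** Inputs from 8.1: COV 24.5% (published Duodopa data) or 23.8% (interim 17.0% × 1.4), Z-alpha 1.96, Z-beta 0.84. The formula is not printed. A paired formula with a small-sample correction, n = (COV × (1.96 + 0.84)/0.20)² + 1.96²/2, gives:

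- COV 24.5%: 11.76 + 1.92 = 13.7, so 14.
- COV 23.8%: 11.10 + 1.92 = 13.0 (13.02), so 14.

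**4. Trying n=18 (COV test).** Section 8.1 prints no SD, expected COV or true ratio for this test. Solving the same formula backwards with 1.65 + 0.84 = 2.49 and correction 1.65²/2 = 1.36:

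- Margin 0.20: SD = 0.20 × √(18 − 1.36)/2.49 = 0.33.
- Margin ln 1.25 = 0.223: SD = 0.223 × √(18 − 1.36)/2.49 = 0.37.

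These are implied values, not figures in the Protocol.

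**5. Power of the within-patient test at n=18.** Paired log-COV difference, limit ln 1.25, true ratio 1, non-central t with 17 df and non-centrality 0.223 × √18/SD = 0.947/SD:

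| SD of paired log-COV difference | one-sided 5% | one-sided 10% |
|---|---|---|
| 0.30 | 92% | 96% |
| 0.35 | 83% | 91% |
| 0.36 | 81% | 90% |
| 0.37 | 79% | 89% |
| 0.40 | 73% | 85% |
| 0.50 | 57% | 71% |

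So at 5%, 18 delivers 80% only if the SD is about 0.36 or less. At SD 0.40 the choice between the two alphas alone moves power from 73% to 85%.

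**6. The literal between-patient reading, for scale only.** Assumptions not in the Protocol: equal true CVs, limit 1.25, n=18, and a correlation between treatments. At correlation 0 the F-test power is P(F17,17 < 1.5625 × the lower 5% point of F17,17) = 22%. For correlated treatments a Pitman-Morgan comparison of variances was simulated:

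| Correlation | one-sided 5% | one-sided 10% |
|---|---|---|
| 0 | 22% | 35% |
| 0.5 | 27% | 40% |
| 0.7 | 34% | 49% |
| 0.8 | 43% | 58% |
| 0.9 | 63-64% | 76-77% |

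**The case against.** The best defence is that only an adjective is wrong. The objective, the primary variable and the derivation agree on within-day variability; the paired t-test and the t-test sample-size model work only with one COV per patient. On that reading nobody would test a between-patient spread, and no power deficit is shown, since 18 is compatible with 80% power. Likewise, the one-sided 90% CI may be loose wording for the upper limit of a two-sided 90% CI, because 8.1 itself pairs 1.65 with a 90% CI. Section 8.1 also says that data from the five interim patients were used, so an SD for the individual COV may exist in the interim report, which is cited but not shown.

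Much of this stands. A reader might infer three stronger things that the documents do not support:

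- *That the trial will test a different question with about 22-43% power.* That range holds only for a variance-comparison test the Protocol never names, at an assumed correlation of 0 to 0.8, and at 5% although the quoted sentence literally means 10%.
- *That the test compares exposure between patients.* No between-patient CV of AUC or mean concentration is defined as a test variable.
- *That 18 was computed from an AUC figure.* A two-sample formula gives 2 × (0.238 × 2.49/0.20)² = 17.6, so 18, but the Protocol does not state that input for this test, and the formula differs from the one that reproduces 14. The match may be chance.

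What the defence does not remove is that the label recurs six times in three places without a definition, that the stated alphas differ, and that the input behind 18 is not printed. Probable intent is not a specified rule.

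**Conclusion.** The inferential wording in the Synopsis, 8.1 and 8.2 contradicts 2.1, 6.1 and the definition in 8.2, and Section 8.2 cannot be carried out as worded. The most plausible explanation is a mislabelled individual COV, not a deliberate test of between-patient spread. The alpha for this primary variable is stated as both 10% and 5%. The sample size of 18 cannot be checked: for the within-patient ratio at one-sided 5%, limit 1.25 and equal true COVs, it is adequate if the SD of the paired log-COV difference is about 0.36 or less, and falls to 73% at 0.40 and 57% at 0.50. The Protocol does not say where that SD lies.

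Power under the literal reading should be quoted only conditionally: about 22-64% at one-sided 5% and 35-77% at 10%, assuming equal true CVs, limit 1.25 and correlation 0 to 0.9. It is below 80% throughout that range, but it describes a reading the rest of the text makes unlikely.

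**What to change.** 1. In the Synopsis, 8.1 and 8.2, replace the intersubject label with: individual (within-patient) COV of levodopa concentration over 2-16 h.
2. In 8.2 and the Synopsis, define the comparison as the within-patient ratio of that COV (s.c./Duodopa and i.v./Duodopa), with non-inferiority concluded if the upper confidence limit is below 1.25. Use the one-sided 5% already in 8.1, that is, the upper limit of a two-sided 90% CI, and remove the one-sided 90% wording.
3. In 8.1, state the SD of the paired log-COV difference and its source, re-run the calculation, and restate the power if 18 does not deliver 80%.

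The cost is wording in three places and one repeated calculation. No new data or procedures are needed. The stated power may turn out less favourable.
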